2.3 The Basis for PTQA

Up to 90% of patients with MDS will receive red cell transfusions during the course of their disease, and many will become chronically dependent on them.⁸ Chronic transfusions also lead to an accumulation of iron that, in turn, can lead to cirrhosis, cardiomyopathy, and progressive endocrine dysfunction.²⁴ Thus, potential overuse of red

PROTOCOL TITLE: A New Paradigm of Transfusion Decision Support for Patients with MDS: Using Peri-Transfusion Quality of Life Assessments (PTQAs)

cell transfusions by patients with MDS not only contributes to critical national blood shortages, such as the one experienced in July 2016,⁹ but also can be physiologically damaging. Moreover, transfusion dependency itself can lead to diminished QOL,^{25,26} and recent work has shown that MDS patients who are at the end of life often avoid hospice because of the potential difficulty receiving red cell transfusions there.^{27,28} One strategy to address these issues is to tailor transfusion only to those patients with MDS who benefit.

During our QUALMS validation study (see Protocol 13-346), we found that while some patients had improved QOL after transfusion, others did not, even at the same level of resulting Hb. We thus propose that a better question than “do MDS patients experience better QOL after transfusions” is “which MDS patients experience better QOL after transfusions.” The best way to determine if a specific patient with MDS benefits from transfusions is to measure the patient’s QOL, transfuse, and assess whether or not QOL improves. Such “peri-transfusion QOL assessment” (PTQA) is a paradigm shift because physicians would not be basing transfusion decisions on Hb level or prior transfusion history but on whether transfusion has an effect on the QOL of an individual patient at that time in their disease course.

[figure not shown]
Recent studies have shown it is possible to collect patient-reported outcomes (PROs) such as QOL and use the results to drive clinical care.^{29,30} One analysis specifically demonstrated PTQA is possible, measuring the effect of red cell transfusions on PROs in an ambulatory oncology population, including 115 transfusion episodes.³¹ Patients were telephoned after 7 days to discuss fatigue, shortness of breath, and overall QOL. Of the total episodes, 71% resulted in at least one improvement, but for 29%, there was none. If there is a similarly sized population of patients with MDS who do not experience improved QOL after transfusions, limiting their transfusion may be of great benefit in terms of reducing ferritin, burden of infusion visits, and overall red cell use.

3.0 Inclusion and Exclusion Criteria

3.1 Research Subject Eligibility Screening

Potential participants will be screened for eligibility using clinic schedule reports or the study-specific Epic Workbench report developed by [name] (see above). Members of the study team at all three sites will be trained on the use of the study-specific Epic report. The report will generate a list of potentially eligible participants that will be further screened for eligibility by a designated member of the study team at each site (RA or RPM).

At DFCI, we will ensure eligibility by following the appropriate SOPs (REGIST-100: Internal Eligibility Checklist & REGIST-104: Using the Eligibility Checklist).

PROTOCOL TITLE: A New Paradigm of Transfusion Decision Support for Patients with MDS:
Using Peri-Transfusion Quality of Life Assessments (PTQAs)

3.2 Inclusion/Exclusion Criteria

Inclusion criteria:

1. Age \geq 18 years of age
2. Patients with MDS, including t-MDS and MDS/MPN
3. Transfusion-naive group: approaching Hb of 8.5 g/dL during enrollment period
 - a. Ideally never-transfused (have never received red cell transfusion)
 - b. If not never-transfused, participants are also eligible for inclusion in this group if they have not been transfused with red cells within last 8 weeks
4. Transfusion-dependent group: Patients with \geq 1 transfusion scheduled during 8-week period prior to enrollment
5. Ability to read and understand English

Exclusion criteria:

1. Age $<$ 18 years
2. Cr $>$ 2
3. Known CHF
4. Unstable Angina
5. Hb level below 7.5 g/dL
6. No plans for potential future outpatient transfusion.

3.3 Special Populations

Our study will exclude members of the following special populations:

- Adults unable to consent
- Individuals who are not yet adults (infants, children, teenagers)
- Pregnant women
- Prisoners

4.0 Study-Wide Number of Subjects

4.1 Accrual Goal

Our study-wide accrual goal is 60 evaluable participants. To reach this accrual goal, we will consent and enroll 90 participants as some participants are not able to complete the protocol due to a variety of reasons (e.g., participant does not end up requiring future transfusions). The 60 evaluable participants will be matched 1:1 to historical controls seen between 2015 and 2017, for a total sample size of 120.

5.0 Study-Wide Recruitment Methods

5.1 NA – Our multicenter study will not be employing recruitment methods that are outside the control of the local sites (e.g., call centers, national advertisements).

5.2 NA

5.3 NA

6.0 Multi-Site Research

6.1 Communication Plan

**PROTOCOL TITLE: A New Paradigm of Transfusion Decision Support for Patients with MDS:
Using Peri-Transfusion Quality of Life Assessments (PTQAs)**

As the lead site, DFCI will communicate study updates to participating sites (YCC and WFB) via phone call or email. For the duration of the study, the Research Project Manager (RPM) will ensure that all sites are using the most current version of the protocol and consent documents. YCC and WFB will be asked to send the DFCI study team all notifications of approval (including IRB approval of initial protocol, continuing reviews, and any study modifications). The DFCI study team will monitor the compliance of participating sites during monthly check-in phone calls. In the event of a study modification, potential modifications to the protocol will be discussed during monthly calls prior to implementation.

The DFCI study team will be responsible for all monitoring activities related to the study across all sites. We will implement a risk-based monitoring approach where monitoring activities will be at the discretion of the sponsor/PI ([name]).

We will monitor accrual during our monthly check-in calls. During these calls, we will ensure that all sites are enrolling between 1-2 patients per month. With regards to data monitoring, the DFCI RPM will review the RedCap database for missing/discrepant data every three months. The consent/eligibility for 10% of participants (2 at each site) will be verified with source documentation by the RPM. This will be done remotely and the participating sites will send the RPM the necessary source documentation.

6.2 As this study is minimal risk, we do not anticipate any problems or reportable events. All other problems, interim results, and study updates will be communicated via our monthly study phone call.

6.3 NA

7.0 Study Timelines

7.1 Study Duration

- Individual subjects will participate in the study for approximately 10 weeks from the time of consent. This includes the completion of the pre-transfusion questionnaire, the post-transfusion questionnaire, and the follow-up survey at 8 weeks after transfusion. We will assess the number of hospitalizations and clinic visits for each participant 8 weeks after the index transfusion.
- We anticipate that it will take approximately 18 months to enroll 90 subjects across all three sites.
- The estimated date for the investigators to complete this study is April 30, 2020.

8.0 Study Endpoints

8.1 Study Outcomes

Primary Endpoints

Subjects will be compared with historical controls (matched for transfusion group; IPSS-R; pre-transfusion Hb; and institution) seen between 2015 and 2017. For the transfusion-naïve, the primary outcome will be receipt of second transfusion (yes/no) within 8 weeks following the index transfusion. For the transfusion-dependent, the primary outcome will be defined as number of units pRBCs received within 8 weeks following the index transfusion. For both groups, we will also compare the number of hospitalizations and clinic visits during the 8 weeks after index transfusion (Table).

Secondary Endpoints

Secondary endpoints include decisional regret, perceptions of care, and perceived stress by the associated scales at two months post-transfusion (Table 1).

Table. Primary and Secondary Outcomes, Measured at Two Months after PTQA

Primary	Presence of second transfusion after PTQA (for those undergoing first transfusion) Number of red cell units used since PTQA (for transfusion-dependent) Number of hospitalizations since PTQA Number of clinic visits since PTQA
Secondary	Decisional Regret Decision Regret Scale. ³² 5-item scale provides indicator of health care decision regret; will be tailored to measure regret about transfusion decisions. Perceptions of Care “About Your Care” Domain of Prior DFCI Survey. We previously developed ³³ a 6-item domain based on the Consumer Assessment of Healthcare Providers and Systems Survey “health status” “access,” and “communication” domains. ³⁴ Perceived Stress PSS-4. ³⁵⁻³⁷ The PSS-4 was designed for use with patients with at least a junior high school education, and takes 3 minutes to complete. It contains four questions about feelings of control and overall stress, with simple response alternatives.

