1.0 Objectives

1.1 Study Aims

The goal of this multi-center study is to determine how to tailor blood transfusion decisions to the quality of life (QOL) changes experienced by individual patients with myelodysplastic syndromes (MDS). We will assess this by piloting a peri-transfusion QOL assessment (PTQA) approach. The PTQA involves administering a QOL questionnaire (see Appendix A) to study participants before and after an upcoming transfusion appointment and comparing QOL scores.

Specific Aim 1

Assess the feasibility of PTQA. We will assess the feasibility of this new paradigm of decision support by determining the enrollment yield as a percentage of all patients approached. We will also assess feasibility by calculating the proportion of enrolled participants who complete both the pre- and post-transfusion the Quality of Life in Myelodysplasia Scale (QUALMS).

Specific Aim 2

Assess the potential usefulness of PTQA in improving clinical and utilization outcomes. We will use medical record review and match our participants to historical controls (matched for transfusion group; IPSS-R; pre-transfusion Hb; and institution) to assess our primary outcomes, which are:

1. The presence of second transfusion after PTQA (for transfusion-naive)
2. The number of red cell units used after PTQA (for transfusion-dependent)
3. The number of hospitalizations after PTQA (for both transfusion groups)
4. The number of clinic visits after PTQA (for both transfusion groups)

Specific Aim 3

Explore the potential impact of PTQA on patient-reported outcomes. At 8 weeks post-transfusion, we will send participants a follow-up questionnaire (see Appendix B) to assess the following secondary outcomes:

1. PTQA utilization
2. Decisional regret
3. Perception of care
4. Perceived stress

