9.4 Data Collection

Data will be collected via medical record reviews, the QUALMS, and several other survey instruments.

Primary medical record review will include:

- Sociodemographic information
- Information regarding patients' MDS diagnosis, including IPSS-R score
- The number/frequency of transfusions prior to index transfusion (for transfusion-dependent patients)
- Hemoglobin level prior to index transfusion

Secondary medical record review will include:

- The presence of a second transfusion since index transfusion (for those who are starting transfusion)
- The number of red cell units used since index transfusion (for those who are transfusion-dependent)
- The number of hospitalizations since index transfusion
- The number of clinic visits since index transfusion

Survey instruments will include:

- The QUALMS to assess pre- and post-transfusion MDS-related QOL (see Appendix A)
- The Decision Regret Scale, "About Your Care" domain of prior DFCI survey, and the PSS-4 to assess secondary outcomes related to decisional regret, perception of care, and perceived stress (see Appendix B)

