11.0 Data Management and Confidentiality

11.1 Data Analysis Plan

Feasibility

Feasibility will be characterized by calculating (1) the proportion of enrolled patients out of all patients approached, and (2) the proportion of patients who completed both the pre- and post-transfusion QUALMS surveys out of all enrolled patients. A convenience sample of 60 evaluable patients will be enrolled to the study. To reach this goal, we will enroll 90 participants total, with the expectation that some patients will not be able to complete the study protocol, despite being eligible at the time of consent (e.g., do not end up requiring future transfusions). If the observed survey completion rate is 50% (i.e. 30/60), then this observed rate is consistent, with 95% confidence, with the true survey completion rate being as low as 38% or as high as 62%.

Clinical and Utilization Outcomes

To be assessed for clinical and utilization outcomes, participants must have completed a pre-transfusion QUALMS, received an index transfusion, and completed a post-transfusion QUALMS. Each of the 60 enrolled evaluable patients will be matched 1:1 to historical controls seen between 2015 and 2017, for a matched sample size of 120 patients total. Subjects will be matched for transfusion group, IPSS-R, pre-transfusion Hb, and institution). Comparative analyses will be conducted separately by transfusion group. For the transfusion-naive, the primary outcome will be receipt of second transfusion (yes/no) within two months following the first transfusion. For the transfusion-dependent, the primary outcome will be defined as number of units pRBCs received within two months following the next transfusion.

For both groups, we will also compare the number of hospitalizations and clinic visits two months after index transfusion (Table).

PTQA Utilization and Patient-Reported Outcomes

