APPENDIX F: STUDY SCHEMA

Identify, Screen, & Recruit Participants

- RA uses study-specific Epic Workbench report to identify potentially eligible patients that are either (1) approaching first transfusion or (2) transfusion-dependent
- RA approaches 75 potentially eligible patients over the course of 15 months (23 at YCC and WFB, 29 at DFCI; goal is to reach 60 completed peri-transfusion quality of life assessments [PTQAs])
- Patients approached for consent discussion at appointment prior to first/next transfusion
- Willing participants consented to study and given study packet, including the QUALMS survey

Peri-Transfusion Quality of Life Assessment (PTQA)

Pre-Transfusion QOL Survey Administration

- RA calls participants with reminder to complete survey on the day prior to transfusion
- Participants fill out QUALMS survey at home on day prior to first/next pRBC transfusion

Post-Transfusion QOL Survey Administration

- On the day of transfusion, consenting participants given a second paper copy of the QUALMS survey with a stamped envelope addressed to appropriate site
- RA calls participants with reminder to complete survey exactly one week post-transfusion
- Participants fill out survey at home exactly one week post-transfusion; asked to mail survey back

Dissemination of PTQA Report

- Once received, second QUALMS survey scored and compared with the first
 - Stable QOL = post-transfusion score within 5 points of pre-transfusion score
 - Improved QOL = post-transfusion score 5 or more points higher than pre-transfusion score
 - Worsened QOL = post-transfusion score 5 or more points lower than pre-transfusion score
- Both patient and provider sent a report with PTQA results
 - Report will include language encouraging patients/providers to use results to inform next transfusion decision
 - Report will specifically suggest future transfusions be halted or decreased in frequency if QOL did not improve

Data Analysis

- Participants compared with historical controls (matched for transfusion group; pre-transfusion Hb; IPSS-R; and institution) seen between 2015 and 2017
 - For newly transfused, primary outcome is receipt of second transfusion (yes/no) within two months after index transfusion
 - For transfusion-dependent, primary outcome is number of units pRBCs received within two months after index transfusion
 - At two months post-transfusion, we will compare number of hospitalizations and clinic visits with number before index transfusion

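### Sections 11.1 and 11.4 disagree on whether participants without the post-transfusion QUALMS enter the primary outcome analysis, and the 9.2 definition leaves those participants without a time zero

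*Protocol*

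**What the plan says.** **Who is analysed.** Protocol 11.1 (Clinical and Utilization Outcomes) sets three conditions for outcome assessment: a pre-transfusion QUALMS, an index transfusion and a post-transfusion QUALMS. It matches 1:1 only the 60 evaluable patients. Section 11.4 covers participants who complete the first survey but not the second. It says their outcomes will be evaluated whether or not they are replaced, because the first survey alone may change decisions. It adds that, if appropriate, a sensitivity analysis will be done in those for whom a report was generated.

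**Time zero.** Section 9.2 defines the index transfusion as one for which both surveys were completed. The second survey is due one week after transfusion, with up to one further week allowed.

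**Start of the outcome window.**
- 8.1 text, naive group: "the primary outcome will be receipt of second transfusion (yes/no) within 8 weeks following the index transfusion". The dependent group's unit count uses the same window.
- 7.1: "We will assess the number of hospitalizations and clinic visits for each participant 8 weeks after the index transfusion".
- 9.4: "The number of red cell units used since index transfusion (for those who are transfusion-dependent".
- Appendix F: "For newly transfused, primary outcome is receipt of second transfusion (yes/no) within two months after index transfusion".
- Aim 2: "The presence of second transfusion after PTQA (for transfusion-naive".
- 8.1 Table: the heading is "Primary and Secondary Outcomes, Measured at Two Months after PTQA", and one row reads "Number of red cell units used since PTQA (for transfusion-dependent".
- 11.1, naive group: "the primary outcome will be receipt of second transfusion (yes/no) within two months following the first transfusion". For the dependent group it counts from the *next* transfusion.

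**The concern.** The main comparison is between participants and matched historical controls, so the rule for who is counted, and from when, has to be single and applicable to both sides. It is neither. An analyst could leave out the survey non-completers and cite 11.1, or include them and cite 11.4, and each choice would have support in the text.

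The two options carry different risks. Leaving non-completers out conditions the participant group on something that happens after time zero: being alive, and well and willing enough to return a survey at day 7-14. No such condition is placed on controls. Including them removes that condition but may dilute an effect that works through the report.

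The mixed time origins add a smaller problem. A clock that starts at PTQA cannot be run in controls, who had none.

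**Working it through.** **1. Analysis set, passages side by side.** Take a participant who completes the first survey, is transfused, and never returns the second.
- 11.1: not assessed for clinical and utilization outcomes.
- 11.4: outcomes evaluated. Report recipients form a sensitivity subset, which implies that the main set is wider.
- 9.2: no index transfusion exists, so the 8-week window in 8.1 has no start.
- 11.1 matching: not evaluable, so no control.

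The direct conflict is 11.1 against 11.4. Section 9.2 conflicts by implication, since it defines a transfusion rather than an analysis set.

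**2. Clock.** The 8.1 text, 7.1, 9.4 and Appendix F agree on the index transfusion. Section 1.1 describes PTQA as surveys before and after transfusion plus comparison of the scores, so it cannot be complete before day 7, or day 14 with the extension. Read literally, Aim 2 and the 8.1 Table start later than the 8.1 text does.

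**3. The plan's own power (11.2).** Inputs: 30 per arm and 5% type I error; I assume two-sided.
- Dependent, 8.0 against 6.5 units, SD 2.0: SE = 2.0 × √(2/30) = 0.516. Power = Φ(1.5/0.516 − 1.96) = Φ(0.945) = 82.8%. Stated: 83%.
- Naive, 100% against 70%, continuity-corrected: pooled SE = √(2 × 0.85 × 0.15/30) = 0.0922; unpooled SE = √(0.70 × 0.30/30) = 0.0837. Power = Φ((0.30 − 1/30 − 1.96 × 0.0922)/0.0837) = 84.8%. Stated: 85%.

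Both reproduce. (Fisher's exact test gives 92.3% for the naive comparison.)

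**4. Price of including non-completers.** Let a share s of participants have no report and show no effect. The difference becomes 1.5 × (1 − s) units, and the naive proportion becomes 1 − 0.30 × (1 − s). The protocol does not give s, so 10% and 20% are assumptions.

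| s | Units difference | Naive proportion | Power at n = 30 per arm: dependent / naive | Power with 30 report recipients kept: dependent / naive |
|---|---|---|---|---|
| 10% | 1.35 | 73% | 74% / 78% | 79% / 84% |
| 20% | 1.20 | 76% | 64% / 71% | 74% / 83% |

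The last column adds the non-completers, each with a control, to 30 report recipients: n = 30/0.9 = 33.3 or 30/0.8 = 37.5 per arm. The formulas are those of step 3.

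**The case against.** **On the clock.** Most of the operative text counts from the index transfusion, and both 8.1 and 11.1 state a window and then refer to the Table, so the Table is best read as a summary of that text. Section 9.1 speaks of the first/next transfusion, so *first* and *next* in 11.1 are most likely names for the index, and 11.1 itself goes on to use the word index. This largely stands: the PTQA wording is probably loose labelling. A reader might infer a second, later follow-up window, or that a naive participant could already count as having had a second transfusion at the index. The documents do not support either firmly. No passage starts a clock at the report, and the second case needs a missed first survey plus a literal reading of *first*. What remains is that nothing in the protocol says the terms are equivalent, and the literal one cannot be used in controls.

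**On the analysis set.** Section 11.4 could be describing a side analysis. Its own wording points the other way, because a sensitivity analysis in report recipients presupposes a main analysis in a larger group, while 11.1 is categorical. Section 11.4 does call death within follow-up rare, which limits the survival part of the response condition but not the willingness and fitness to respond.

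**On power.** A reader might infer that 11.2 overstates power because the report arrives one to two weeks into the window. That does not follow. The stated powers are right for the differences they name, those differences can be read as net of any lag, and the lag belongs to the index-based clock that should be kept.

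**Conclusion.** The contradiction between 11.1 and 11.4 is real, is in the current text, and decides who is in the primary comparison. Section 9.2 makes it worse by tying time zero to a later survey. It should be fixed, at small cost. The inconsistent time origin is a lesser wording fault.

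If 9.2 and 11.1 govern, participants meet a response condition at day 7-14 that controls do not. A reader might infer that this favours PTQA. The documents give neither the share of non-completers nor how they differ, so size and direction are both unknown.

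The power figures for the wider set rest on an assumed 10% or 20% without a report, no effect at all in them, a two-sided 5% test and the 11.2 inputs. The no-effect assumption is pessimistic, since 11.4 itself allows that the first survey may act alone. The 30-per-arm column is also the less favourable case: 4.1 enrols 90 to reach 60 evaluable and 11.4 will try to replace non-completers, though it warns this may not be feasible.

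**What to change.** 1. In 9.2, define the index transfusion without the later survey, for example as the first transfusion for which the pre-transfusion QUALMS was completed. This fits 11.4, which already regards those who never complete the first survey as not enrolled.
2. Use one phrase, within 8 weeks after the index transfusion, in Aim 2, the 8.1 text and Table, 11.1 and Appendix F.
3. Name one main analysis set. Following 11.4 is preferable: everyone with an index transfusion, each matched to a control, with report recipients as the sensitivity analysis. Make *evaluable* in 4.1 and 11.1 match. If 11.1 is kept instead, say that participants were selected on response at day 7-14 and controls were not.

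**Cost.** Wording changes, with no new follow-up. If 30 report recipients per group are kept, about 3 to 4 (10%) or 7 to 8 (20%) further controls per group need chart review. The statistical price is the possible dilution tabulated above. A supportive landmark analysis from a fixed day, applied alike to participants and controls, is optional and not needed to resolve the contradiction.

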11.2 Power Analysis

Transfusion-naive patients: With a type I error of 5% and a sample size of 60 transfusion-naive patients total (30 PTQA versus 30 historical controls), we will have 85% power to detect changes in the proportion of transfusion-naive patients receiving second transfusion from 100% to 70%.

Transfusion-dependent patients: With a type I error rate of 5% and a sample size of 60 transfusion-dependent patients total (30 PTQA versus 30 historical controls), we will have 83% power to detect a decrease in mean number of units received from 8.0 to 6.5 if the standard deviation is 2.0 units.

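### Units given at the index transfusion are neither listed for chart review nor matched, although they can delay the next transfusion; recording and adjusting for them is a cheap improvement

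*Protocol*

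**What the plan says.** For the transfusion-dependent, Protocol 8.1 defines the outcome by what follows the index: "For the transfusion-dependent, the primary outcome will be defined as number of units pRBCs received within 8 weeks following the index transfusion". Section 11.1 words it similarly: "number of units pRBCs received within two months following the next transfusion". For the transfusion-naive, the outcome is whether a second transfusion occurs in the same period.

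The comparison is not randomised: "Each of the 60 enrolled evaluable patients will be matched 1:1 to historical controls seen between 2015 and 2017". The controls are "matched for transfusion group; IPSS-R; pre-transfusion Hb; and institution". Specific Aim 2 in 1.1, section 11.1 and the study schema in Appendix F name the same four factors.

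The chart review in 9.4 lists, before the index, the haemoglobin level and "The number/frequency of transfusions prior to index transfusion (for transfusion-dependent patients"). After the index it lists "The number of red cell units used since index transfusion (for those who are transfusion-dependent"). Neither list names the units given at the index. For the transfusion-naive, no unit count is listed at all.

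Section 9.2 places the second QUALMS about one week after the index transfusion, with the PTQA report after that. Section 11.2 sizes the dependent comparison, with 30 participants against 30 controls, for "a decrease in mean number of units received from 8.0 to 6.5 if the standard deviation is 2.0 units".

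**The concern.** The outcome period starts after the index transfusion, but what was given at the index can affect when the next one is needed. The report comes later and cannot have changed the index dose. That makes index dose a baseline variable: adjusting for it removes no PTQA effect, and ignoring it leaves a possible confounder.

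Participants and controls are treated years apart. Section 11.1 also says that the consensus haemoglobin data will go to providers before the study starts, which the controls' providers did not have. A difference in units per visit is therefore possible, in either direction. If an extra index unit delays later transfusion, a larger index dose in participants would lower both transfusion outcomes with no PTQA effect, and a smaller one would conceal a real effect.

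Matching on pre-transfusion haemoglobin does not settle this, because patients at the same level can receive different numbers of units.

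**Working it through.** **1. The plan's own figure.** The inputs from 11.2 are a difference of 8.0 − 6.5 = 1.5 units, SD 2.0, 30 per group and alpha 5%.

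SE = 2.0 × √(2/30) = 0.516. Power = Φ(1.5/0.516 − 1.96) = 82.8%. A two-sample t-test gives 81.5%. The stated 83% reproduces as a two-sided test (one-sided would be 89.6%), so 1.5 units with this SE is a fair yardstick.

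**2. Later units removed per extra index unit.** The protocol does not give this. Take a need of 1 unit per week, which is 8.0 units over 8 weeks, an index dose d, and later transfusions of m units. If the next transfusion comes when the previous dose is used up, mean later units are about 8 − d + m/2. A mass-balance simulation (between-patient CV 25%, assumed) agrees.

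| Assumed pattern | d = 1 | d = 2 | d = 3 | Later units removed per index unit |
|---|---|---|---|---|
| Need-triggered, later doses always 2 units | 8.0 | 7.0 | 6.0 | 1.0 |
| Need-triggered, same dose at every visit (m = d) | 7.5 | 7.0 | 6.5 | 0.5 |
| Fixed two-week calendar, later doses always 2 units | 8.0 | 8.0 | 8.0 | 0 |

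With weekly checks in the second pattern, the step from 1 to 2 units disappears (6.9 against 7.0). The offset is therefore an assumption with a range of 0 to 1.

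**3. Effect on the dependent comparison.** Bias b = offset × mean imbalance. With an offset of 0 to 1 and an imbalance of 0.25 to 0.5 unit (assumed), b runs from 0 to 0.5 unit.

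- False-positive rate if PTQA has no effect = Φ(b/0.516 − 1.96) + Φ(−b/0.516 − 1.96).
- Power for a true 1.5-unit effect if the imbalance runs the other way = Φ((1.5 − b)/0.516 − 1.96).

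| b (units) | Share of 1.5 | False-positive rate | Power, opposite direction |
|---|---|---|---|
| 0 | 0% | 5% | 82.8% |
| 0.25 | 17% | 7.7% | 67.7% |
| 0.5 | 33% | 16.2% | 49.1% |

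**4. Transfusion-naive group.** Assume log-normal weekly need, and a second transfusion within 8 weeks if need is at least d/8 units per week. Then P = Φ(ln(median × 8/d)/log-SD).

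- Median 0.5, log-SD 0.5: Φ(ln 4/0.5) = 99.7% after 1 unit and Φ(ln 2/0.5) = 91.7% after 2 units. The gap is 8 points per full unit. An average imbalance of 0.25 to 0.5 unit gives 0.25 × 8 = 2 to 0.5 × 8 = 4 points. This case lies closest to the 100% control rate in 11.2.
- Median 0.25, log-SD 0.7: 84% and 50%. The gap is 34 points per full unit, or 8.5 to 17 points for the same imbalance. Here the control rate is well below 100%.

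The target in 11.2 is a 30-point difference (100% to 70%).

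**The case against.** **The size is assumed throughout.** No section relates index units to later units, and none shows that index dose differs between the two periods or in which direction. Sections 3.2 and 9.2 speak of scheduled transfusions and appointments, which leans towards the calendar pattern with an offset of 0. A change in units per visit would plausibly affect every visit, not only the index. Patients with greater need may receive more units both at the index and later, so the association could even be positive. All of this stands, and it is why the figures are given as ranges.

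**The gap may be one of wording.** The lists in 9.4 need not be exhaustive, the dose sits in the same transfusion record, and covariates are commonly left to an analysis plan, which is not shown here. This stands in part: the units are not listed, which is less than saying they will not be collected. But the outcome, the matching factors and the chart-review fields are fixed in this protocol. An analysis plan cannot adjust for a field that was never abstracted.

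**It is a pilot, and other factors are unmatched too.** Prior transfusion number or frequency is already collected and may predict later use better. That is fair, but it is listed for the dependent group only and counts transfusions, not units.

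**Conclusion.** The structural point holds. A variable fixed before the report, and able to affect both primary transfusion outcomes, is not counted, matched or listed for abstraction. This is a worthwhile, inexpensive improvement, not a demonstrated bias.

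For the dependent group, the worst case within the assumed ranges is a third of the target effect, and the best case is no bias. For the naive group, the shift is small against the 30-point target near the protocol's own control rate, and larger only if need is lower.

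A reader might infer three stronger things that the protocol does not support:

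- That each extra index unit removes about one later unit. This is the upper end of the range and needs need-triggered transfusion with unchanged later doses.
- That participants will in fact have a different index dose. Nothing in the protocol shows this.
- That the naive outcome could shift by more than its 30-point target. Gaps of that order (34 points in the second case) arise only when every patient in one group receives a full unit more, and in scenarios far from a 100% control rate.

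**What to change.** - **9.4:** list the number of red cell units given at the index transfusion as baseline data, for participants and controls in both transfusion groups.
- **8.1:** state that index units are not counted in the outcome.
- **11.1:** adjust both primary transfusion comparisons for index units, or at least report each with and without that adjustment. The data then supply the slope, and no offset or direction need be assumed.

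The cost is one more field from records already under review and one degree of freedom per comparison. No patients are added.

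Matching on index units, or reporting a total that includes them, is not needed. Matching would make controls harder to find. The total would add units that the report could not have changed.
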